### **3.6 Risks and benefits**

The risk to subjects in this trial will be minimized by compliance with the eligibility criteria and study procedures, close clinical monitoring, and the provision of rescue options.

Experience in the PARADIGM-HF trial; both in the run-in phase as well as the double-blind randomization phase indicated that the major risks associated with the treatment of sacubitril/valsartan are renal dysfunction, hyperkalemia, and hypotension. Results from the TITRATION study indicated that subjects whom are ACEi or ARB naïve are at an increased risk of experiencing these adverse events.

In this study, the risk of experiencing renal dysfunction, hyperkalemia, and hypotension are mitigated in this study by appropriate up-titration of the drug at weeks 2, 4, 8, 10, and 12. The risks are further mitigated by appropriate inclusion and exclusion criteria. Subjects are excluded if they have a potassium > 5.2 mmol/l at screening.

Sacubitril/valsartan may also cause angioedema. The risk of developing angioedema is increased if subjects take both an ACEi and sacubitril/valsartan. To decrease this risk, all subjects will undergo a 36 hour wash out period before entering the randomized phase epoch and before continuing into the open-label treatment epoch to minimize the interaction between an ACEi and sacubitril/valsartan in potentiating the development of angioedema.

All subjects will be allowed to continue receiving the rest of their background cardiovascular (CV) medications throughout the study. Subjects will be randomized to study treatment only after the investigator has confirmed the subject is on stable treatment with guideline-directed therapy for heart failure with reduced ejection fraction (HFrEF), other than ACEis and ARBs, which will ensure that subjects are receiving appropriate treatment for their heart failure.

In the PARADIGM-HF study, sacubitril/valsartan reduced the risk of cardiovascular (CV) death, HF hospitalization and due to these significant results, sacubitril/valsartan is now indicated to reduce these risks in subjects with chronic heart failure (NYHA class II-IV) and reduced ejection fraction.

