#### **4.2 Exclusion criteria**

Subjects fulfilling any of the following criteria are not eligible for inclusion in this study. No additional exclusions may be applied by the investigator, in order to ensure that the study population will be representative of all eligible subjects.

1. Subjects with a history of hypersensitivity to any of the study drugs, including history of hypersensitivity to drugs of similar chemical classes, or allergy to ACEIs, ARBs, or NEP inhibitors as well as known or suspected contraindications to the study drugs.
2. Subjects with a history of angioedema drug related or otherwise
3. Subjects with symptomatic hypotension or systolic blood pressure  $<$ 100 mmHg at screening or  $<$ 95 mmHg at randomization.
4. Subjects with any conditions in skin or upper extremities which would limit the ability to tolerate a wrist-worn actigraphy device on the nondominant arm for 24 hours/day for the duration of the study.
5. Subjects unwilling or unable to wear and operate the study measurement devices for the phases required.
6. Subjects who are currently hospitalized, or were discharged from the hospital within 4 weeks prior to enrollment.
7. Subjects who are already taking sacubitril/valsartan
8. Subjects who are nonambulatory or use mobility assistive devices such as motorized devices, wheelchairs, or walkers. The use of canes for stability while ambulating is acceptable.
9. Subjects with physical activity impairment primarily due to conditions other than heart failure such as:
  - Exertional angina
  - inflammatory or degenerative joint disease
  - gout
  - peripheral vascular disease

- neurologic diseases affecting activity or mobility

10. Subjects with nontypical circadian behavioral patterns (for example: shift workers actively rotating shifts, subjects with non-24-hour sleep wake disorder as result of blindness)

11. Subjects with tremor, rigor or mobility limitations affecting the nondominant arm (e.g. due to Parkinson's disease, joint contractures, paralysis, injury etc.)

12. Subjects with chronic obstructive pulmonary disease (COPD) who require supplemental oxygen.

13. Subjects using a continuous positive airway pressure (CPAP) devices or similar technology for treatment of sleep disorders

14. Subjects unwilling or unable to refrain from the use of prescription and/or over the counter (OTC) sleep aids for the duration of the study

15. Subjects with body mass index (BMI) > 35

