16. Subjects with chronic persistent atrial fibrillation.

17. Subjects with diabetes who are taking aliskiren.

18. Subjects receiving nesiritide

19. Subjects taking bile acid sequestering agents such as cholestyramine or colestipol (to avoid interference with study drug absorption).

20. Subjects who are enrolled or participating as a subject in any other clinical trial involving any investigational agent or investigational device within 30 days before screening.

21. Subjects with a potassium > 5.2 mEq/L at screening.

22. Subject with a history of malignancy of any organ system who have a life expectancy of less than 1 year.

23. Pregnant or nursing (lactating) women, where pregnancy is defined as the state of a female after conception and until the termination of gestation, confirmed by a positive human chorionic gonadotropin (hCG) laboratory test.

24. Women of child-bearing potential, defined as all women physiologically capable of becoming pregnant, unless they are using highly effective methods of contraception during dosing and for 7 days after stopping of study medication. Highly effective contraception methods include:

- a. Total abstinence (when this is in line with the preferred and usual lifestyle of the subject). Periodic abstinence (e.g., calendar, ovulation, symptothermal, post-ovulation methods) and withdrawal are not acceptable methods of contraception
- b. Female sterilization (have had surgical bilateral oophorectomy with or without hysterectomy) total hysterectomy or tubal ligation at least six weeks before taking investigational drug. In case of oophorectomy alone, only when the reproductive status of the woman has been confirmed by follow up hormone level assessment
- c. Male sterilization (at least 6 months prior to screening). For female subjects on the study, the vasectomized male partner should be the sole partner for that subject
- d. Use of oral, (estrogen and progesterone), injected or implanted hormonal methods of contraception or placement of an intrauterine device (IUD) or intrauterine system (IUS) or other forms of hormonal contraception that have comparable efficacy (failure rate <1%), for example hormone vaginal ring or transdermal hormone contraception.

In case of use of oral contraception women should have been stable on the same pill for a minimum of 3 months before taking investigational drug.

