#### **Adjustment of study drug dose level**

**Table 5-7 Safety and tolerability guidance for dose adjustments**

Parameter	Criteria
Potassium level	$K > 5.3\text{ mEq/L}$
Kidney function	

• eGFR reduction <math>\geq 35\%</math> compared to baseline; OR, serum creatinine of <math>\geq 0.5\text{mg/dl}</math> with at least a 25% decrease in eGFR

Blood pressure	

• No symptomatic hypotension or SBP <math>< 90\text{ mmHg}</math>

Adverse events (AEs) or conditions	

• No postural symptoms or any conditions that preclude continuation according to the investigator's judgment

Every attempt should be made to maintain subjects on target study drug Dose Level 3 for as long as possible throughout the study. If, however, in the opinion of the investigator, a patient is unable to tolerate the protocol-specified target dose, the investigator will manage the patient's treatment according to the below guidelines:

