2.1.1 General definitions

Study treatment

Patients will receive either sacubitril/valsartan or enalapril during the first 8 weeks of the study. Study treatment will refer to either of these two drugs.

Baseline

The last non-missing assessment prior to or on the start date of study treatment (randomization date for patients not treated) will be used as baseline, unless otherwise specified.

Date of first administration of study treatment

Randomized treatment phase: The date of first administration of study treatment in the randomized treatment phase is defined as the first date a dose of study treatment is administered and recorded on the Dosage Administration Record - At Visit (Visit 3) electronic case report form (eCRF).

Open-label extension phase: The date of first administration of study treatment in the open-label extension phase is defined as the first date a dose of sacubitril/valsartan is administered in the open-label extension phase and recorded on the Dosage Administration Record - Summary eCRF.

Date of last administration of study treatment

Randomized treatment phase: The date of last administration of study treatment in the randomized treatment phase is defined as the last date a dose of study treatment is administered in the randomized treatment phase and recorded on the Double-Blind Phase Disposition eCRF (for patients continuing into the open-label extension phase) or the Study Completion/Discontinuation eCRF (for patients not continuing into the open-label extension phase).

Open-label extension phase: The date of last administration of study treatment in the open-label extension phase is defined as the last date a dose of sacubitril/valsartan is administered in the open-label extension phase and recorded on the Dosage Administration Record - Summary eCRF.

Study day

The study day describes the day of the assessment relative to the date of randomization.

The study day will be calculated as the difference between the date of assessment and the date of randomization plus 1. If the date of assessment is prior to the date of randomization, the study day will be negative and will be calculated as the difference between the date of the assessment and the date of randomization.

Randomized treatment phase

Assessments performed at Weeks 2, 4, or 8 (e.g., vital signs) are assigned to the randomized treatment phase for summarization purposes. Unscheduled assessments are not assigned to a phase.

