5.3.2 Notable laboratory values

Hematology

Red blood cell (RBC) count >50% increase, >20% decrease

Hemoglobin	>50% increase, >20% decrease
Hematocrit	>50% increase, >20% decrease
White blood cell (WBC) count	>50% increase, >50% decrease
Platelet count	>75% increase, >50% decrease

Blood Chemistry

Alanine aminotransferase (ALT) (SGPT)	>150% increase
Aspartate aminotransferase (AST) (SGOT)	>150% increase
Blood urea nitrogen (BUN)	>50% increase
Creatinine	>50% increase
Total bilirubin	>100% increase
Alkaline phosphatase	>100% increase
Potassium	>20% increase, >20% decrease
Chloride	>10% increase, >10% decrease
Calcium	>10% increase, >10% decrease
Uric acid	>50% increase

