5.4 Vital signs

5.4.1 Notable vital sign values

Systolic blood pressure	<90 mmHg and decrease of >20 mmHg from baseline
	>180 mmHg and increase of >20 mmHg from baseline
Diastolic blood pressure	<50 mmHg and decrease of >15 mmHg from baseline
	>105 mmHg and increase of >15 mmHg from baseline
Pulse	<50 bpm and decrease of > 15 bpm from baseline
	>120 bpm and increase of >15 bpm from baseline
Weight	>7% decrease, >7% increase

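### The SAP's notable-value rules under-count systolic pressure below 90 mmHg in patients who start below 110, and its potassium flag does not measure hyperkalemia

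*SAP*

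**What the plan says.** **Systolic pressure.** SAP 5.4.1 defines a notable low value as "<90 mmHg and decrease of >20 mmHg from baseline"; both conditions must hold. SAP 2.8.4.1 tabulates patients with notable vital signs by treatment phase. It also plans by-visit descriptive summaries by treatment group, which under SAP 2.1 include minimum and maximum. There is no shift table for vital signs. Protocol 4.2 excludes patients below 100 mmHg at screening or below 95 at randomization.

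**Potassium.** SAP 5.3.2 gives the rule as ">20% increase, >20% decrease" with no absolute level. It repeats Protocol Appendix 1. SAP 2.8.3 also plans low/normal/high shift tables to the most extreme post-baseline value, and SAP 5.3.1 rules out conversion to CTCAE grades. Protocol 4.2 excludes "Subjects with a potassium > 5.2 mEq/L at screening".

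**Baseline.** SAP 2.1.1 uses "The last non-missing assessment prior to or on the start date of study treatment".

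**The protocol's own absolute levels.** Table 5-7, "Safety and tolerability guidance for dose adjustments", names systolic pressure below 90 mmHg, with no change condition, and potassium above 5.3 mEq/L.

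**Why these two measures.** Protocol 3.6 states that "the major risks associated with the treatment of sacubitril/valsartan are renal dysfunction, hyperkalemia, and hypotension". Protocol 9.5.2 rests the safety assessment mainly on the frequency of adverse events, serious adverse events and laboratory abnormalities, without inferential analysis.

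**The concern.** A rule that requires both a level and a change is hardest to meet for patients who start close to the level. Here those are the patients with the lowest pressure at entry. Someone who goes from 100 to 82 mmHg is under the Table 5-7 figure and yet is tabulated as having no notable value.

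A percent-change rule for potassium has a related weakness. A patient who starts high needs a very high value to be flagged, while one who starts low is flagged at a value under every potassium level quoted above.

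The notable tables are the only planned counts of patients against fixed vital-sign limits. Because the safety analysis is descriptive, a reader will take these counts as the incidence of low pressure and of disturbed potassium. They do not measure either at the levels the protocol itself uses.

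**Working it through.** The plan states no figure that depends on these rules, so there is nothing to reproduce. The check is threshold arithmetic.

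**1. Systolic limit.** Inputs are the SAP 5.4.1 rule and the entry floor of 95 at randomization (Protocol 4.2). With baseline B, a value is flagged only if it is below min(90, B − 20).

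| Baseline (mmHg) | Flagged only below | Under 90 but not flagged |
|---|---|---|
| 95 | 75 | 75 to 89 |
| 100 | 80 | 80 to 89 |
| 105 | 85 | 85 to 89 |
| 110 or more | 90 | none |

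The second condition can only remove cases from those under 90. The direction of the error is therefore certain.

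**2. What else would count these patients.**
- By-visit minima can show that such a value occurred, but not in how many patients.
- SAP 2.3.1 lists symptomatic hypotension as a reason for not achieving Dose Level 3.
- The adverse-event tables (SAP 2.8.1.3) include low pressure only if it was reported as an event. Under Protocol 7.1 an abnormal test result is an event only if it causes signs or symptoms, is considered clinically significant, or requires therapy.

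An asymptomatic reading under 90 with a fall of 20 mmHg or less, not reported as an event, is counted in no visible table.

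**3. Potassium limit.** Inputs are the SAP 5.3.2 rule and the 5.3 level in Table 5-7. With baseline B, a high flag needs a value above 1.2 × B.

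| Baseline (mEq/L) | Flagged high only above |
|---|---|
| 3.5 | 4.20 |
| 4.0 | 4.80 |
| 4.5 | 5.40 |
| 5.0 | 6.00 |
| 5.2 | 6.24 |

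The crossing point is 5.3 / 1.2 = 4.42. Above that baseline, values over 5.3 can be missed; below it, values at or under 5.3 are flagged. The 5.2 limit applies at screening. Laboratory tests are repeated at Visit 3 (Protocol 6.5.5.2), so baseline can exceed 5.2 and the cut-off can exceed 6.24.

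**4. Share of patients with a stricter systolic limit.** The documents give no baseline distribution. Assume a normal distribution with mean 118 to 126 and SD 15 to 17, cut at 95. The share is [Φ((110 − m)/s) − Φ((95 − m)/s)] / [1 − Φ((95 − m)/s)].
- m = 126, s = 15: (0.1431 − 0.0194) / 0.9806 = 12.6%.
- m = 118, s = 17: (0.3190 − 0.0880) / 0.9120 = 25.3%.

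These are patients whose limit is below 90, not missed events.

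**5. Illustration of missed values.** This is a simulation with one post-baseline value per patient and normal changes independent of baseline; every distribution is assumed.
- Systolic (baseline mean 115 to 125, SD 12 to 15, cut at 95; change mean −5 to −8, SD 10 to 13): the rule misses 21% to 61% of values under 90.
- Potassium (baseline mean 4.2 to 4.6, SD 0.3 to 0.4, cut at 5.2; change mean 0 to +0.2, SD 0.35 to 0.45): it misses 42% to 95% of values over 5.3, and 21% to 82% of its high flags are at or under 5.3.
- Net potassium count: 7.9% flagged against 4.8% over 5.3 in one scenario (mean 4.2, SD 0.3, change +0.2, SD 0.45), and 0.5% against 6.0% in another (mean 4.6, SD 0.4, change 0, SD 0.35). It goes either way.

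**The case against.** **Other outputs cover part of this.** The shift table classes each patient's most extreme potassium as low, normal or high whatever the percent change. The adverse-event tables and the Dose Level 3 reasons add counts of hyperkalemia and symptomatic hypotension. This stands. A reader might infer that the tables as a whole under-report hyperkalemia, but the documents do not support that: the flag errs in both directions and other tables exist. What remains is that the shift table has one high class, so it does not separate a value just over the reference limit from one above 6.

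**The potassium rule is the protocol's own.** Appendix 1 calls these changes clinically notable, while Table 5-7 guides dose adjustment and is not a reporting standard. This is fair. The plan does not contradict itself here, and reporting against Table 5-7 as well is a judgement about usefulness. The systolic rule differs: the visible part of Appendix 1 lists laboratory limits only, so that rule appears only in the SAP.

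**Patients near the limits can still be flagged.** True: below 75 to 80 mmHg from a baseline of 95 to 100, or above 6.24 mEq/L from 5.2. The rule is stricter for them, not blind.

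**Both arms get the same rule.** A reader might infer that the comparison of arms is made to look more favourable to one drug, or less different. Nothing in the documents shows this. No arm-specific distribution is given, and neither the direction nor the size of any distortion can be derived.

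**Unscheduled values may already count.** SAP 2.1.1 leaves unscheduled assessments out of the visit-assigned summaries, but for notable values it takes every assessment within the phase's date interval. That reading appears right and needs only confirmation.

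**Conclusion.** The concern holds in two limited parts.

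- **Systolic pressure:** the notable table under-counts readings under 90 mmHg among patients with baseline below 110. This follows from the rule and needs no assumption. Its size does: about 13% to 25% of patients would have the stricter limit under the assumed baseline distributions.
- **Potassium:** the flag measures relative change, not hyperkalemia. It departs from the 5.3 mEq/L level on both sides of a baseline of about 4.42, and the net effect on the count is undetermined. What counts as a normal potassium depends on the central laboratory's range, which the documents do not give.

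Primary and secondary efficacy analyses are unaffected. This is an inexpensive improvement to the descriptive safety tables for two of the three major risks the protocol names.

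**What to change.** In SAP 2.8.3, 2.8.4.1, 5.3.2 and 5.4.1, keep the existing notable rows and add, by arm and treatment phase, the number and percentage of patients with:

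- any post-baseline systolic pressure below 90 mmHg, without a change condition;
- any post-baseline potassium above 5.3 mEq/L, optionally with one higher cut.

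Both levels are those of Protocol Table 5-7, used here for tabulation only; no dose or management rule changes. Add one sentence confirming that the phase definition for notable values in SAP 2.1.1 includes unscheduled assessments.

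The cost is SAP wording and two or three extra table rows from data already collected. The one downside is that the reported incidence of low systolic pressure and high potassium will be higher than the notable rows alone may suggest, so the new rows should stand beside the existing ones with their definitions stated.

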5.5 Statistical models

5.5.1 Primary analysis

The null hypothesis for the primary analysis is the difference between the sacubitril/valsartan and enalapril groups in the mean change from baseline in mean activity count at Week 8 is equal to zero. An ANCOVA model will be used. The model will have the change from baseline as the dependent variable with treatment as a fixed effect factor and the baseline value as a covariate. The general form for the ANCOVA model is:

$$y_{ij} = \mu + \alpha_i + \beta(x_{ij} - \bar{x}) + \epsilon_{ij}$$

where i indexes treatment group and j indexes patient within treatment group. PROC MIXED in SAS will be used for the analysis (refer to the SAP TFL shells document for additional details).

5.5.2 Key secondary analysis

The analysis of secondary endpoints will use the same approach as described for the analysis of the primary endpoint in Section 5.5.1.

5.6 Rule of exclusion criteria of analysis sets

Table 1 Protocol deviations that cause patients to be excluded

Deviation ID	Description of Deviation	Exclusion in Analyses
NA	NA	NA

Table 2 Patient Classification

Analysis Set	Protocol deviation ID that cause patients to be excluded	Non-protocol deviation criteria that cause patients to be excluded
RS	NA	Not randomized
FAS	NA	Not in RS; Have not received study treatment but inadvertently randomized
SS	NA	No double-blind study treatment received

6 Reference

Chen M, Kianifard F (2000) A nonparametric procedure associated with a clinically meaningful efficacy measure. *Biostatistics*; 1(3):293-298.

[REDACTED]

